### **10.3. Interim analysis**

Since participants will receive standard of care, with additional biopsies based on PCaVision for this study which can be considered of minimal risk and without infringement in clinical decision making, no interim analysis will be performed.

An interim analysis will be performed when the data of 50% of the planned total sample size is available for review. We will determine the prevalence of csPCa in our cohort and re-perform the sample size calculation while leaving all other parameters the same. Moreover, we will evaluate the frequency of discarded scans due to quality issues. If more patients are needed based on one of these recalculations, the total sample size will be adjusted accordingly. The total sample size will not be lowered as a result of this re-calculation.

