#### **4.5. Sample size calculation**

The sample size calculation is based on demonstrating non-inferiority between the detection rate of clinically significant cancer from the PCaVision pathway and the MRI pathway using patients as the unit of analysis and data from the fully paired design.

The detection rates of PCa (GG $\geq$ 2) based on MRI and PCaVision targeted biopsies are expected to be around 30%. These values are based on the detection rates of PCa (GG $\geq$ 2) reported by Mannaerts et al., 2020 [30] and Grey et al., 2022 [43], which were found to be 29% and 30% with MRI and 28% and 26% with 2D CUDI (older version of PCaVision), respectively.

The non-inferiority margin is set to 5% absolute difference in detection rate. The expected proportion of discordant pairs is 10%. This proportion expresses the degree in which PCaVision and MRI disagree with respect to detecting and missing significant cancers in a paired design. This parameter is relevant when analysing data from a paired study design. A smaller percentage of discordant pairs will lower the required sample size. In the studies of Mannaerts et al., 2020 [30] and Grey et al., 2022 [43], the percentage discordant pairs were 10.1% and 8.9%, respectively.

Our assumptions of the sample size calculations are therefore the following: an expected detection rate of 30% for both imaging techniques, a non-inferiority margin of 5% points and a percentage discordance between both imaging techniques of 10%, a one-sided type 1 error of 2.5% (as recommended by the European Medicines Agency) and a power of 80%. This leads to a required total sample size of 350 patients.. This is the total number of men who need to undergo both PCaVision and MRI, and produce images of sufficient quality, followed by targeted biopsies if indicated. This sample size calculation was performed according to Liu et al., 2002 [47] and Hintze, 2008 [48].

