With both imaging pathways, we expect a certain percentage of men in whom either PCaVision or MRI or both produce image quality that is insufficient to perform targeted biopsies upon, or technical issues when performing targeted biopsies. The primary, paired analyses will be based on men having sufficient quality images and targeted biopsies from both imaging techniques. During the development of the PCaVision algorithm, insufficient scans were manually excluded to ensure optimal quality for training purposes. Currently, PCaVision incorporates an automated image quality check to guarantee sufficient signal and quality. To compensate for discarded scans due to quality issues, 25% additional patients will be included. The total sample size will therefore be 438 subjects to obtain 350 evaluable patients in the paired analysis.

As we would like to include PCa patients from 5 clinical centres, the patient number target per centre is 80, with a range of 40-120.

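### Section 10.3 both rules out and orders an interim analysis, and its evaluability check counts only discarded scans, so it can miss a shortfall below 350 evaluable men

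*Combined protocol and SAP*

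**What the plan says.** **Section 10.3.** The first paragraph argues from standard of care and minimal risk that "no interim analysis will be performed". The second paragraph begins "An interim analysis will be performed when the data of 50% of the planned total sample size is available for review". At that point the team will determine csPCa prevalence and "re-perform the sample size calculation while leaving all other parameters the same". It continues: "Moreover, we will evaluate the frequency of discarded scans due to quality issues". The consequence is: "If more patients are needed based on one of these recalculations, the total sample size will be adjusted accordingly". The total may not be lowered.

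**Section 4.5.** The calculation requires 350 evaluable men, and 25% is added for discarded scans, giving 438. The same section restricts the primary paired analysis to men with adequate images and targeted biopsies from both techniques. Beside poor images it names a second expected cause of loss: "or technical issues when performing targeted biopsies".

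**Sections 8.4, 8.5 and 10.** Section 8.4, on withdrawal, excludes from analysis men with poor imaging or other technical problems with ultrasound, MRI or biopsy. Section 8.5 says in one sentence that withdrawn subjects are replaced. The opening of section 10 again defines the paired dataset by images and subsequent targeted biopsies for both techniques.

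**The concern.** There are two linked problems.

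1. Only the second paragraph of section 10.3 provides for a recalculated total above 438. The first says that no such step exists. Section 12.8 treats departures from the statistical plan as deviations, so whichever paragraph a team follows, it departs from the other.
2. The check meant to protect the evaluable number is narrower than the definition of an evaluable man. A loss that section 4.5 itself expects, technical failure of the targeted biopsy, is outside the check. The review could report that 438 is enough while the paired set is heading below 350.

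At stake are a clear authority to enlarge the trial and the planned 80% power of the primary non-inferiority comparison.

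**Working it through.** **Inputs (section 4.5).** Detection rate 30% in both pathways, so true difference 0; margin 0.05; discordance 0.10 (0.05 in each direction); "a one-sided type 1 error of 2.5% (as recommended by the European Medicines Agency) and a power of 80"%; 350 evaluable; 438 enrolled.

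**Reproducing the plan's figures.** The paired score test uses the restricted maximum-likelihood variance at the margin, v0 = 0.11642:

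n = (1.960 × √0.11642 + 0.842 × √0.10)² / 0.05² = 349.6, so 350.

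Enrolment: 350 × 1.25 = 437.5, so 438. Both figures reproduce.

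**Tolerable loss.** 350/438 = 79.9%. The plan can lose 438 − 350 = 88 men, and 88/438 = 20.1%, from all causes together. If 15% of men are lost to scans, 5.1% is left for everything else. At 20%, 0.09% is left.

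**What a scan-only check would see.** The documents give no rate for scan loss or for any other loss, so every rate below is an assumption. Losses are fractions of enrolled men and are added.

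- Scan-only projection = 438 × (1 − scan loss)
- Evaluable = 438 × (1 − scan loss − other loss)
- Total needed = 350 / (1 − scan loss − other loss)
- Power: exact multinomial power of the score test under the inputs above

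| Scan loss | Other loss | Scan-only projection | Evaluable | Exact power | Total needed |
|---|---|---|---|---|---|
| 15% | 5% | 372 | 350 | 81.3% | 438 |
| 20% | 2.5% | 350 | 339 | 80.4% | 452 |
| 15% | 10% | 372 | 328 | 78.9% | 467 |
| 20% | 5% | 350 | 328 | 78.9% | 467 |
| 20% | 10% | 350 | 307 | 75.4% | 500 |

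The unrounded evaluable numbers are 350.4, 339.4, 328.5, 328.5 and 306.6. Exact power moves in small steps and is not strictly monotone: at 306 it is 75.6%.

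In every row the scan-only projection is at least 350, so no increase is triggered. In the last four rows the paired set is below 350.

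**Power by the planning formula.** Power = Φ[(0.05√n − 1.960 × √0.11642)/√0.10] gives about 80% at 350, 78.7% at 339, 77.3% at 328 and 74.4% at 307. This is slightly lower than exact power, with the same pattern.

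**Can the other recalculation fill the gap?** In the formula that reproduces 350, the required number depends on discordance and margin, not on prevalence. With discordance held at 10%, updating prevalence returns 350 again. The evaluability check is then the only part of the review that can raise the total.

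**The case against.** **The two paragraphs may not truly conflict.** The first gives a safety reason, nearly the one section 9.5 gives for having no DSMB. The second describes only a sample-size review and mentions no test of the pathway difference. The natural reading is therefore no safety or efficacy look, but a re-estimation of size. This is fair, and it makes the repair one of wording. It does not remove the conflict, because both paragraphs use the same term without that distinction.

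**A reader might infer that the first paragraph leaves the trial with no protection against high failure rates.** The documents do not support that. The 25% inflation in section 4.5 and the replacement rule in section 8.5 do not depend on section 10.3.

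**Replacement may already cover biopsy failures.** Technical exclusions are described in section 8.4 under withdrawal, and section 8.5 follows directly. On that reading these men are replaced and the shortfall disappears. Against it, full replacement would make the 25% largely redundant, and section 8.5 speaks only of withdrawal. The text is open on this point. True withdrawals are plainly replaced, so they should not be counted as lost.

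**The gap exists only in a band.** With small losses 438 suffices, and with scan loss above 20.1% the existing check already triggers. Both points stand. An increase sized on scan loss alone could still be too small, however. At an assumed 25% scan loss plus 5% other loss it would set 350/0.75 = 467 men, of whom 467 × 0.70 = 327 would be evaluable.

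**Conclusion.** The inconsistency in section 10.3 is a plain textual fact and must be reconciled. The evaluability check can miss a shortfall, because it omits a loss that the plan itself lists.

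The size is modest and conditional. It rests on loss rates that the documents do not give, and on technical exclusions not being replaced under section 8.5. Over the assumed range the result runs from no shortfall (15% plus 5%) to 307 evaluable men and 75.4% exact power (20% plus 10%), against 81.3% at 350.

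Two stronger readings should be resisted:

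- A reader might infer that any paired set below 350 misses the 80% target. By exact calculation power is still 80.4% at 339, and at 328 it is about one point under target.
- A reader might infer that the trial will be underpowered. Without observed loss rates the documents do not show that. They show only that the planned check could fail to notice it.

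**What to change.** Replace both paragraphs of section 10.3 with one statement containing the following:

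- There is no interim test of the difference between pathways.
- A sample-size review takes place at 50% of the planned total.
- The review sets total N = (required evaluable number, currently 350) / (observed fraction of enrolled men who enter the paired set).
- The fraction counts every unreplaced loss: scan failures, targeted-biopsy failures, and any withdrawals not replaced under section 8.5.
- N is never lowered.

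While 350 is the required number, an increase is triggered when total unreplaced loss exceeds 20.1%. Define the trigger through the formula rather than as a fixed percentage, because it moves if the required number changes. State in section 8.5 whether men excluded for technical reasons are replaced.

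The cost is protocol wording. Inadequate images and targeted biopsies are already to be compared between pathways as a secondary endpoint (sections 8.1.2 and 10.2), so the counts should be collected anyway. The documents do not list the eCRF fields, so confirm that the reason for leaving the paired set is recorded. The downside is that the review may call for somewhat more men, as the plan already allows.

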## **11. ETHICAL CONSIDERATIONS**

### **11.1 Regulation statement**

This study will be conducted according to the principles of the Declaration of Helsinki (Fortaleza, Brazil, October 2013), and in accordance with the Medical Research Involving

Human Subjects ACT (WMO), Good Clinical Practice (ICH-GCP) and in compliance with the approved research protocol.

The clinical investigation shall not begin until the required approval/ favourable opinion from the EC and regulatory authority have been obtained.

Any additional requirements imposed by the EC or regulatory authority shall also be followed.

## **11.2 Recruitment and consent**

Patients will present themselves at the outpatient clinic where their urologist will assess the possibility of study participation. When a patient is eligible for participation, study information will be provided both orally and in writing (participant information and consent form) by the treating physician. Next to informing the patient about the study, this physician also provides the Patient Information Folder (PIF) to the patient. The local investigator will then perform the Informed Consent Form (ICF) procedure. If the patient is willing to participate in the study, informed consent will be asked by the local investigator and signed by both the local investigator and the patient. Patients will be informed that they can withdraw at any time for any reason if they wish to do so without any consequences. The patient will have two days or more to consider their consent.

## **11.3 Benefits and risks assessment, group relatedness**

There could be a potential benefit for the patients participating in this study when a clinically significant cancer is detected by targeted biopsies based on PCaVision that would otherwise have been missed by both MRI and systematic biopsies. Furthermore, the results of this study may be important for future patients suspected of prostate cancer. If PCaVision is sufficiently accurate, it could coexist with MRI as the central imaging strategies which would lead to a more streamlined and more cost-effective diagnostic work-up as the ultrasound examination is less costly and can be performed by urologists followed by targeted biopsies in the same session. If PCaVision is sufficiently sensitive, systematic biopsies after a negative ultrasound examination could even be omitted in the future, thereby reducing the burden associated with unnecessary biopsies.

Additional targeted biopsies could be performed because of the identification of PCa based on PCaVision imaging. These extra biopsies carry a small risk of haemorrhage and infection. There is also a small, anticipated risk for participants (with a risk classification of negligible risk) associated with the administration of ultrasound contrast agent. However, adverse events caused by the ultrasound contrast agent appear to be transient, mild, and rare. These mostly consist of transient alteration of taste, local pain at the injection site and facial or general flush. In rare cases allergic reaction is described.

In conclusion, although the potential benefit for the patient is small, we also believe that the burden and risk associated with participation in this study is limited. Patients will be informed about this risk before the study, and it will be described in the study information.

## **11.4 Compensation for injury**

The sponsor/investigator has a liability insurance which is in accordance with article 7 of the WMO. The sponsor (also) has an insurance which is in accordance with the legal requirements in the Netherlands (Article 7 WMO). This insurance provides cover for damage to research subjects through injury or death caused by the study.

The insurance applies to the damage that becomes apparent during the study or within 4 years after the end of the study.

## **11.5 Incentives**

This study is free of charge for every patient. Angiogenesis Analytics will reimburse patients participating in this study with travel expenses incurred by participation in the study. This involves maximally 1 extra study-required visit at any of the participating centres. Otherwise, there are no special incentives.

# **12. ADMINISTRATIVE ASPECTS, MONITORING AND PUBLICATION**

## **12.1 Handling and storage of data and documents**

Data collection and analysis will be monitored according to GCP. Data will be collected in an electronic data management system: Castor Electronic Data Capture, from CIWIT BV, Amsterdam, the Netherlands, website <https://www.castoredc.com>. All data collected in Castor will be stored on servers located the Netherlands hosted by TRUE ([www.true.nl](http://www.true.nl)). All data will be handled confidentially. Each participant will be recoded and be given a case number. A subject identification code list can be used if it is necessary to trace data to an individual subject. The principal investigator will safeguard the key to the code. All handling of personal data complies with the GDPR (general data protection regulation) (in Dutch: Algemene verordening gegevensbescherming (AVG)).

### **12.1.1 Case Report Forms/Electronic Case Report Forms**

An eCRF will be used in this study. A CRF is required and should be completed for each included subject. The investigator has ultimate responsibility for the collection and reporting of all clinical, and safety data entered on the CRFs and any other data collection forms (source documents) and ensuring that they are accurate, authentic/original, attributable, complete, consistent, legible, timely (contemporaneous), enduring and available when required. Any corrections to entries made in the CRFs, source documents must be dated, initialed and explained (if necessary) and should not obscure the original entry. In case of electronic data record, the corrections history will be maintained by an audit trail.

In most cases, the source documents are the hospital's or the physician's subject chart. In these cases data collected on the CRFs must match the data in those charts.

In some cases, the CRF, or part of the CRF, may also serve as source documents. In these cases, a document should be available at the investigator's site as well as at Angiogenesis

Analytics and clearly identify those data that will be recorded in the CRF, and for which the CRF will stand as the source document.

### **12.1.2. Procedures**

All data from the examinations and investigations in this study will be transferred to media provided by the subsidizing party and collected at the time of eCRF collection. The Principal Investigator will manage and maintain the study database throughout the investigation. At the conclusion of the investigation, the database will then be locked and data transferred for analysis. There will be a documented record of data transfer and measures in place for the recovery of original information after transfer.

The database maintained by the Principal Investigator, shall be validated and secured according to the sponsor standard operating procedures. The pseudonymized data to which the subsidizing party will have access include:

- age (in years)
- PSA value
- rectal examination results
- prostate volume
- dates of appointments and procedures
- US images + results
- MRI images + results
- pathology report of prostate biopsies

Any study data released shall be done according to the publication policy.

No tissue material originating from the subjects after the biopsy procedures shall be stored as part of the study and no tissue material shall be transferred to the sponsor. So, tissue storage common practice will not be affected by our study. Tissue storage will be according to local hospital protocol.

### **12.1.3. Privacy Procedure**

Subject privacy is maintained and protected as follows.

- All personal data is encrypted and the coding is presented as “PCaVision -Study Site Acronym - Subject Number”
- Only the principal investigator has access to the key of this encryption
- Source documents and any other personally identifiable information can be accessed by:
  - principal investigators of participating centres
  - auditor
  - national authorities, for example: Inspectie Gezondheidszorg en Jeugd (IGJ)

- Test subjects will not be approached again after completion of the study (for example for further research or follow up)
- No tissue material will be transferred to the sponsor, only the pseudonymized pathology report

#### **12.1.4. Procedure for locking and storing database**

After study completion and data cleaning the Castor database will be locked.

Data will be preserved for the minimum duration of 15 years.

#### **12.1.5. Data retention**

All records pertaining to the study (e.g. data report forms, informed consent forms, source documents, IRB correspondence, study ID code list and other study documentation) will be retained at the site.

Data and all appropriate documentation will be stored according to guidelines for 15 years after the completion of the trial, depending on country-specific regulations.

### **12.2 Monitoring and Quality Assurance**

The adherence to the protocol and the quality of completeness of the collected data will be monitored on a regular basis. We will plan an initiation monitor visit before the inclusion of the first patient in each center and an interim monitor visit each 3 months due to negligible patient risk.

Monitoring will be risk-based. In the Risk Management File, 5 out of 7 identified medium-level risks are related to an operator error; 1 is related to algorithm performance and 1 to an allergic response of the patient in response to the US contrast agent. As a result, there will be an extra focus in the monitoring visits on operator performance, algorithm performance and the (correct) use of the US contrast agent.

### **12.3 Amendments**

Amendments are changes made to the research after a favourable opinion by the accredited METC has been given. All amendments will be notified to the METC that gave a favourable opinion. Non-substantial amendments will not be notified to the accredited METC and the competent authority but will be recorded and filed by the sponsor.

### **12.4 Annual progress report**

The sponsor/investigator will submit a summary of the progress of the trial to the accredited METC once a year. Information will be provided on the date of inclusion of the first subject, numbers of subjects included and numbers of subjects that have completed the trial, serious adverse events/ serious adverse reactions, other problems, and amendments.

## **12.5 Temporary halt and (prematurely) end of study report**

The investigator/sponsor will notify the accredited METC of the end of the study within a period of 8 weeks. The end of the study is defined as the last patient's last visit.

The sponsor will notify the METC immediately of a temporary halt of the study, including the reason of such an action.

In case the study is ended prematurely, the sponsor will notify the accredited METC within 15 days, including the reasons for the premature termination.

Within one year after the end of the study, the investigator/sponsor will submit a final study report with the results of the study, including any publications/abstracts of the study, to the accredited METC.

## **12.6 Public disclosure and publication policy**

This is an investigator-initiated trial, all results all eligible for publication.

The study will be registered at ClinicalTrials.gov before the inclusion of the first patient.

## **12.7 Sponsor Activities**

Sponsor representatives will perform all activities related to data collection.

## **12.8 Deviations**

Protocol deviations are any alteration or deviation from the approved research plan including the original statistical analysis plan as defined in the study protocol. This includes equipment failures during study procedures.

The investigator is **not allowed to deviate from the CIP without prior approval** from the EC. However, deviations from the CIP may proceed without prior approval of the sponsor and the EC, if they are required to protect the rights, safety and well-being of human subjects under emergency circumstances. Such deviations shall be documented and reported to the sponsor and the EC as soon as possible;

If the researcher anticipates that there will be future requests for the same deviation, then the protocol will be amended (and such amendments must be approved by the REC/IRB).

If the study objectives and procedure or cohort changes or the study changes from non-medical to medical, this generates a new study (not an amendment).

